7.3 TREATMENT COMPLIANCE

Treatment compliance will be reported based on calculation as described in CTP section 4.3. Only descriptive statistics are planned for this section of the report. Treatment non-compliance is defined as any enrolled patients having taken at least one dose of study medication with an overall compliance rate not between 80% and 120% inclusive. Overall compliance is calculated based on unweighted average of study drug compliance rate at each visit during the treatment period. For the patients who discontinued the study treatment prematurely only the visits on or before premature discontinuation will be used for the calculation of overall compliance.

Summary statistics of overall compliance in the treated set will be given for the number of subjects as well as the corresponding percentage with compliance in the categories <80%, 80% - 120%, >120%, missing.

7.4 PRIMARY ENDPOINT(S)

7.4.1 Primary analysis of the primary endpoint(s)

The primary endpoint is the occurrence of treatment emergent adverse events (TEAEs) up to Week 288. The primary analysis will be based on the exposure adjusted rate of patients reporting a treatment emergent adverse event (TEAE) up to Week 288.

Exposure-adjusted adverse event incidence rates will be calculated using the following approach:

- The incidence rate (per 100 subject years) of a selected adverse event (also known as the incidence density rate or person-time incidence rate) is defined as the number of subjects experiencing the adverse event per treatment group during the time at risk divided by the total time of subjects at risk in that treatment group to contribute an event to the analysis multiplied by 100 (per 100 subject years), where for each subject and each TEAE preferred term:

$$\text{Time at risk [subject years]} = (\text{date of first onset of AE} - \text{study drug start date} + 1) / 365.25$$

If, for a subject, no treatment emergent adverse event occurred for the preferred term, then the time at risk will be censored at the minimum of (date of death; drug stop date + 7 days; last contact date).

- For each AE, the incidence rate will therefore be calculated as:

$$\text{Incidence rate [per 100 subject years (pt-yrs)]} = 100 * \text{number of subjects with TEAE} / \text{Total TEAE-specific time at risk [subject years].}$$

Exact 95% confidence intervals (CI) around the observed AE incidence rate will also be provided using exact Poisson regression.

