5.2.6 Assessment of adverse events

5.2.6.1 Definitions of AEs

5.2.6.1.1 Adverse event

An AE is defined as any untoward medical occurrence in a patient or clinical investigation subject administered a medicinal product and which does not necessarily have to have a causal relationship with this treatment.

An AE can therefore be any unfavourable and unintended sign (including an abnormal laboratory finding), symptom, or disease temporally associated with the use of a medicinal product, whether or not considered related to the medicinal product.

The following should also be recorded as an AE in the CRF and BI SAE form (if applicable):

- Worsening of the underlying disease or of other pre-existing conditions
- Changes in vital signs, ECG, physical examination and laboratory test results, if they are judged clinically relevant by the investigator.

If such abnormalities already exist prior to trial inclusion, they will be considered as baseline conditions and should be collected in the eCRF only.

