7.3.4 Safety analyses

Adverse events will be coded using the Medical Dictionary for Drug Regulatory Activities (MedDRA). Standard BI summary tables and listings will be produced. All adverse events with an onset between start of treatment and end of the REP, a period of 7 days after the last dose of trial medication, will be assigned to the on-treatment period for evaluation.

All treated patients will be included in the safety analysis. In general, safety analyses will be descriptive in nature and will be based on BI standards. No hypothesis testing is planned.

Statistical analysis and reporting of adverse events will concentrate on treatment-emergent adverse events, i.e. all adverse events occurring between start of treatment and end of the REP. Adverse events that start before first drug intake and deteriorate under treatment will also be considered as 'treatment-emergent'.

Exposure-adjusted adverse event incidence rates (per the primary endpoint) will be calculated using the following approach:

• The incidence rate (per 100 subject years) of a selected adverse event (also known as the incidence density rate or person-time incidence rate) is defined as the number of subjects experiencing the adverse event per treatment group during the time at risk divided by the total time of subjects at risk in that treatment group to contribute an event to the analysis multiplied by 100 (per 100 subject years), where:

Time at risk [subject years] = (date of onset of AE – study drug start date + 1) / 365.25

If, for a subject, no treatment emergent adverse event occurred, then the time at risk will be censored at the minimum of (date of death; drug stop date + 28 days; last contact date).

For each AE, the incidence rate will therefore be calculated as:

Incidence rate [per 100 subject years (pt-yrs)] = 100 * number of subjects with TEAE / Total TEAE-specific time at risk [subject years].

Exact 95% confidence intervals (CI) around the observed AE incidence rate will also be provided.

Page 58 of 84

Frequency, severity, and causal relationship of adverse events will be tabulated by system organ class and preferred term after coding according to the current version of the Medical Dictionary for Drug Regulatory Activities (MedDRA) at database lock.

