6. GENERAL ANALYSIS DEFINITIONS

6.1 TREATMENT(S)

All patients need to complete the preceding Phase II psoriasis Trial 1407-0030 and meet entry criteria for this study.

Two groups of patients are to be entered into this trial, including up to (approximately) 180 patients entered in the original trial 1407-0030 protocol (now Part 1) and approximately 90 patients entered in an extended dose-ranging segment, now Part 2 of the amended trial 1407-0030 protocol. Actual numbers of subjects entering the extension trial are to be determined by response in the preceding study.

In the first group (Part 1), patients will be considered eligible to participate in this long-term extension trial upon completing the trial 1407-0030 Week 24 end-of-treatment visit with a \geq PASI50 response. BI 730357 dose levels of up to 200 mg *q.d.* are to be administered under fasting conditions to patients in this group, reflecting the dose levels evaluated during Part 1 of trial 1407-0030.

- Patients entering the extension trial will remain on their blinded BI 730357 dose treatment from the preceding trial until the open label period of 1407-0005 begins at Visit 2/Week 12.
- At Visit 2/Week 12, patients presently assigned to double blind treatment of placebo, 25 mg, 50 mg, and 100 mg will be reassigned to the 100 mg open label dose, and patients presently assigned to the double blind treatment of 200 mg will be reassigned to 200 mg open label dose.

In the second patient group (Part 2), patients will be considered eligible to participate in this trial upon completing the trial 1407-0030 Week 12 end-of-treatment visit with a \geq PASI50 response or perceived patient improvement, at the discretion of the Investigator. Patients are to be considered eligible only if also without ongoing AEs consistent with intolerance of trial medication (including gastric intolerance) that in the opinion of the investigator would compromise the safety of the patient.

.

- All patients entering the extension trial are to be assigned at Visit 1 to receive open-label treatment with 400 mg *q.d.* (fed), the anticipated therapeutic BI 730357 dose.

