It is expected that Visit 1 of trial 1407-0005 will be performed on the same day of the EOT Visit of trial 1407-0030 in both patient groups. In the event that patients completing Part 2 of trial 1407-0030 are not able to be entered immediately into the extension trial due to administrative reasons (e.g., pending protocol approval, availability of trial medication), Visit 1 of the extension trial may be delayed for no more than 16 weeks.

The treatment period in this trial will be approximately 6 years.

Figure 6.1: 1

Trial 1407-0005 dose assignment/reassignment for patients entering from Part 1 of trial 1407-0030

[figure not shown]
[figure not shown]

Figure 6.1: 2

Trial 1407-0005 dose assignment for patients entering from Part 2 and continuing from Part 1 of trial 1407-0030

Dose selection at Week 12 is based on the safety and tolerability data from the SRD Trial 1407.1 and the MRD Trial 1407-0002, and will be contingent on DMC evaluation of all available data from Phase II trial 1407-0030. For patients entering from Part 1 of trial 1407-0030, if an unacceptable risk regarding the safety of the 200 mg dose level is reported by the DMC, the open label BI 730357 dose assignments beginning at Week 12, is to be altered to assign all patients to the 100 mg *q.d.* dose group.

All patients entering from Part 2 of trial 1407-0030 are to receive the 400 mg *q.d.* dose, as long as no unacceptable risks are identified during Part 2 of trial 1407-0030. Once Part 2 patients begin enrolling in this trial, existing patients receiving 100 mg *q.d.* in this trial will be given the option to titrate up to the 200 g *q.d.* dose, if the investigator determines that the Patients may benefit from the higher dose.

The first Part 2 patients enrolled in this study on December 10, 2020 and at that time all Part 1 patients had been in the study more than 12 weeks and had titrated to 100 mg *q.d.*

Subjects will be analyzed according to the treatment to which they were treated. The following study periods based on actual start and stop dates of study treatment administration are defined as follow.

Table 6.1: 1 Definition of Treatment Periods

Analysing Treatment Period	Start Date	Stop Date
Screening [#]	NA	NA
On-treatment*	Date/Time of the first administration of trial treatment	Date of the last administration of trial treatment + REP
Follow-up	Date of the last administration of trial treatment + REP+1 day	Date of the last per protocol visit

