Patients in the 1407-0030 trial that fulfil the criteria for rollover will be asked to participate in this extension trial. Upon their agreement, they will immediately enter the treatment phase. Therefore, no screening period is defined in this trial.

* Within the On-treatment period, it can be divided into Period 1 (first 12 weeks) and Period 2 (after 12 weeks) for patients from part 1 of the 1407-0030 trial.

For the main safety analyses, Adverse Events (AEs) for patients who rolled over from Part 1 of trial 1407-0030 will be classified to one of the following time periods: “first 12 weeks of treatment”, “second treatment period”, or “follow up”. Section 7.3.4 of the protocol specifies that, all AEs and laboratory assessments with an onset between start of treatment and end of the residual effect period (REP), a period of 7 days after the last dose of trial medication for this trial, will be assigned to the “on-treatment” period for evaluation.

Detailed rules for assigning AEs to these time periods based on the onset dates of the AEs for patients who rolled over from Part 1 of the 1407-0030 trial are listed below (such AEs will be classified as new-onset TEAEs):

- If date of Start of Treatment visit in trial (1407-0005) \leq AE onset date $<$ date of first intake after week 12 re-assignment, then the AE is assigned to “first 12 weeks of treatment”.

If an AE occurs on the day of week 12 visit, actual time between AE onset and study medication taken will be compared to determine AE time period (first 12 weeks, second treatment period).

If the subject discontinues before the day of week 12 visit, date of first intake after week 12 re-assignment will be missing, the AE will still be assigned to “first 12 weeks of treatment”.

- If date of first intake after week 12 re-assignment \leq AE onset date \leq date of last intake + 7 days, then the AE is assigned to “second treatment period”.

Section 7.3.4 of the protocol specifies that adverse events that start before first drug intake and deteriorate under treatment will also be considered as ‘treatment emergent’. Worsening will be determined by a more severe grade according to Rheumatology Common Toxicity Criteria (RCTC) Version 2.0 Detailed rules for assigning such AEs of patients from Part 1 of the 1407-0030 trial to these time periods based on the onset dates and worsening dates of the AEs are listed below (such AEs such be classified as worsening-severity TEAEs):

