- If AE onset date \leq date of End of Treatment visit in the preceding trial (1407-0030) < AE worsening date < date of first intake after week 12 re-assignment, then the AE is assigned to “first 12 weeks of treatment”.

If an AE worsening occurs on the day of week 12 visit, actual time between AE onset and study medication taken will be compared to determine AE time period (first 12 weeks, second treatment period).

If the subject discontinues before the day of week 12 visit, date of first intake after week 12 re-assignment will be missing, the AE worsening will still be assigned to “first 12 weeks of treatment”.

- If date of first intake after week 12 re-assignment \leq AE worsening date \leq date of last intake + 7 days, then the AE is assigned to “second treatment period”.

For patients who rolled over from Part 1 of the 1407-0030 trial if the onset date of an AE occurs prior to Week 12 and continues beyond Week 12 with a worsening RCTC grade after Week 12 then the AE will be captured as a TEAE both during the first 12-week period of 1407-0005 (as a new-onset TEAE) and during the second treatment period (beyond Week 12, as a worsening-TEAE).

Because there is no scheduled titration for patients who rolled over from Part 2 of trial 1407-0030 adverse events will only be summarized for the entire treatment period and will not be summarized for the first 12 weeks and after 12 weeks for these patients.

Due to differing doses, differing titration schedules and different timeframe for entering this study between patients from part 1 and part 2 of trial 1407_00030, several sets of adverse event analyses, each consisting of 11 summaries, will be presented:

- Events up to 12 weeks for patients who rolled over from Part 1 of trial 1407_00030 with treatment columns BI 25 mg, BI 50 mg, BI 100 mg and BI 200 mg
- Events after 12 weeks for patients who rolled over from Part 1 of trial 1407_00030

with treatment columns BI 25 mg/BI 100 mg, BI 50 mg/BI 100 mg, BI 100 mg/BI 100 mg and BI 200 mg/ BI 200mg.

- All events for patients who rolled over from Part 2 of trial 1407-0030 with treatment column BI 400 mg
- All events from all patients who rolled over from trial 1407-0030 (part 1 and part 2 combined) where events are classified under the treatment at onset in 1407-0005 with treatment columns BI 25 mg, BI 50 mg, BI 100 mg, BI 200 mg and BI 400 mg

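### The time-at-risk formula in SAP 7.4.1 gives zero or negative person-time to a TEAE that began before the first 1407-0005 dose and worsened on treatment, if the event keeps its original onset date

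*SAP*

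**What the plan says.** The primary analysis is the exposure-adjusted rate of patients with a TEAE. In SAP 7.4.1 the time at risk of a subject with the event runs from the study drug start date to the "date of first onset of AE", plus one day, divided by 365.25. Protocol 7.3.4 has the same structure: "Time at risk [subject years] = (date of onset of AE" minus the start date, plus one. The censoring rule applies only to subjects with no TEAE (in the SAP, none for that preferred term).

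The TEAE definition is wider than new onsets. Protocol 7.3.4 states: "Adverse events that start before first drug intake and deteriorate under treatment will also be considered as" treatment-emergent. SAP 6.1 repeats this and adds "Worsening will be determined by a more severe grade according to Rheumatology Common Toxicity Criteria (RCTC) Version 2.0". For Part 1 it then assigns these events, which it classes as worsening-severity TEAEs, to periods using two separate dates. The onset is on or before, and the worsening after, the last treatment visit of 1407-0030: "date of End of Treatment visit in the preceding trial (1407-0030) < AE worsening date".

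**The concern.** The numerator admits events by their worsening date, while the denominator closes each subject's time at the onset date. For a carried-in event the onset lies before the clock starts. The subject then counts as a case but adds no person-time, or takes some away from the total contributed by others. The rate for that preferred term is overstated.

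Negative person-time is never a valid contribution to a rate or to its exact Poisson interval. SAP 7.4.1 states no floor at zero, no substitute date and no exclusion. A programmer would have to apply the formula literally or pick a remedy, and the remedies give different rates.

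**Working it through.** No figure in the documents depends on this formula, so there is nothing to reproduce.

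**Inputs**
- Formula: SAP 7.4.1 and Protocol 7.3.4. The start date is taken as the first 1407-0005 dose, following the on-treatment start in SAP Table 6.1: 1. Section 7.4.1 does not define it.
- Part 1: entry "upon completing the trial 1407-0030 Week 24 end-of-treatment visit", so 24 weeks = 168 days of prior treatment, with same-day entry expected.
- Part 2: 12 weeks = 84 days of prior treatment. "Visit 1 of the extension trial may be delayed for no more than 16 weeks", which adds up to 112 days.
- Planned group sizes (Protocol synopsis): 25 mg, 0 to 40 patients; 50 mg, 0 to 80.

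**Step 1: can the case arise?** Yes. Exclusion criterion 14 bars only ongoing intolerance AEs that the investigator thinks would compromise safety. Other ongoing AEs can carry over.

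**Step 2: the formula.** With onset d days before the first dose, time at risk = (−d + 1)/365.25 = (1 − d)/365.25 years.

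| Onset | d | Time at risk (years) |
|---|---|---|
| Day before first dose | 1 | 0 |
| Part 1, first day of 1407-0030 | 168 | −167/365.25 = −0.457 |
| Part 2, first day of 1407-0030 | 84 | −83/365.25 = −0.227 |
| Part 2, with full entry delay | 84 + 112 = 196 | −195/365.25 = −0.534 |

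These values are nominal. An earlier onset or a late visit would go lower. The Part 2 rows rest on the general rule in Protocol 7.3.4 only.

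With the worsening date, an event on study day w contributes w/365.25, which is at least one day. The shortfall per affected subject is therefore (w + d − 1)/365.25 years.

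**Step 3: size over full follow-up.** All inputs are assumed except the follow-up length: 90 patients; 5 new-onset cases at 0.5 year; k carried-in cases worsening on day 91 (0.249 year), all with d = 168; no dropout. Follow-up is (2016 + 7)/365.25 = 5.539 years. Numerators are equal, so the inflation is the ratio of denominators.
- k = 1: with worsening date 84 × 5.539 + 2.5 + 0.249 = 468.00; as written 84 × 5.539 + 2.5 − 0.457 = 467.29. Inflation 0.15%.
- k = 5: with worsening date 80 × 5.539 + 2.5 + 1.246 = 446.84; as written 80 × 5.539 + 2.5 − 2.286 = 443.31. Inflation 0.80%.

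If follow-up averaged only 1 year, the same inputs give 0.8% (k = 1) and 4.4% (k = 5).

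**Step 4: size in a short-exposure column.** SAP 6.1 plans exposure-adjusted rates in the display by dose at onset, with 25 mg and 50 mg columns. Part 1 patients leave those doses at Week 12, so, if person-time is split by dose, each holds about 84 days. Assumed: 3 cases of one preferred term, on-treatment events at mid-period (42/365.25 = 0.115 year), carried-in onset at d = 168.

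For 40 patients, time with worsening dates is 37 × 84/365.25 + 3 × 0.115 = 8.85 years, a rate of 33.9 per 100 patient-years. With one carried-in case, time as written is 8.51 + 2 × 0.115 − 0.457 = 8.28 years, a rate of 36.2.

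| Patients | Rate with worsening date | As written: 1, 2, 3 carried-in cases | Inflation |
|---|---|---|---|
| 40 | 33.9 | 36.2, 38.9, 42.0 | 7%, 15%, 24% |
| 20 | 70.5 | 81.5, 96.5, 118.2 | 16%, 37%, 68% |

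These are worst cases, because every carried-in onset is put on the first day of 1407-0030. Intervals at 3 events are wide: for 40 patients, 7.0 to 99.0 with worsening dates, and 8.7 to 122.8 as written with three carried-in cases.

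**The case against.** The strongest defence is that the plan, read as a whole, means onset as a TEAE. SAP 6.1 classifies events by treatment at onset within 1407-0005, SAP 7.8.1 speaks of the dose at the onset of the TEAE, and a worsening after Week 12 is captured as a TEAE of its own. SAP 7.4.1 also counts subjects who have the event during the time at risk, which negative time contradicts. This shows what was probably intended. It does not change the formula, which names first onset of the AE, and no text puts the worsening date in its place.

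Second, SAP 7.8.1 refers to a sponsor guideline on summarising AEs, and its reference entry is blacked out in the public copy. It may cover such events. That cannot be checked, and the rule stated for the primary analysis would still be wrong as it stands.

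Third, recording practice. Protocol 5.2.6.1.1 asks sites to record as an AE "Worsening of the underlying disease or of other pre-existing conditions". If a worsening becomes a new record with its own onset date, time at risk is positive and the problem disappears. This point stands as a condition on the finding. The two-date rule in SAP 6.1 points the other way, but it is written for Part 1 only.

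Fourth, the analysis is descriptive and the effect over planned follow-up is very small. This also stands, and it sets the severity.

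**Conclusion.** Wrong as written, and minor. If a worsened AE keeps its original onset date, the stated formula gives its subject (1 − d)/365.25 years, nominally 0 to −0.46 years in Part 1. The number of such AEs is not known. In the illustration the inflation is below 1% over full follow-up without dropout. It could be material only where exposure is short, in the 25 mg and 50 mg columns. There it could make low doses look worse than the long-exposure columns in a descriptive comparison. No hypothesis is tested, so no formal conclusion changes.

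A reader might infer more, and the documents do not support it:
- *That Part 2 is shown to be affected in the same way.* The Part 2 values of −0.23 and −0.53 years follow only if the general rule in Protocol 7.3.4 is applied with the original onset date kept. SAP 6.1 has no two-date rule for Part 2.
- *That Part 2 rates could be heavily inflated over a 12-week window.* SAP 6.1 summarises Part 2 AEs for the entire treatment period, so no such short display is planned. Over full follow-up the Step 3 inputs give 0.1% to 0.5% (d = 84) and 0.2% to 0.9% (d = 196).
- *That the SAP 7.8.1 sentence sending pre-dose AEs to screening removes these events.* It refers to Section 6.1 for detail, where they are TEAEs and no screening period is defined. It is probably leftover text.

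**What to change.** In SAP 7.4.1, replace the first-onset date with the date on which the event first qualifies as a TEAE for that subject and preferred term. This is the onset date for new-onset TEAEs and the date of first on-treatment worsening for worsening-severity TEAEs. State that the rule holds for both parts, and assign the event to the dose taken on that date. Every case then contributes at least one day.

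The cost is about one sentence. SAP 6.1 already needs worsening dates for Part 1. Assuming Part 2 uses the same CRF, no new data are required.

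Two clarifications are optional and not part of the finding: limiting the screening sentence in SAP 7.8.1 to AEs that do not worsen on treatment, and naming in SAP 6.1 the AEs that begin between the 1407-0030 end-of-treatment visit and a delayed Visit 1.
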